Omega-3 Fatty Acids as First-Line Treatment in Pediatric Depression

Statistical Analysis Plan for [name], [name]

[name] ([contact])

[name]

Version 1.0 of May 23, 2022

List of abbreviations

AD	antidepressant
AE	adverse event
CDRS-R	Children's Depression Rating Scale - Revised
DIKJ	Children's Depression Inventory (Depressionsinventar für Kinder und Jugendliche)
EPA	eicosapentaenoic acid
KIDscreen-CAT-27	quality of life questionnaire
pMDD	pediatric major depressive disorder
SIQ-Jr	Suicide Ideation Questionnaire-Junior
SUSAR	Suspected Unexpected Serious Adverse Reaction

Introduction

1 Type of trial

This is a 36-week multi-center 1:1 randomized, double-blind, placebo-controlled, two-armed, parallel group study investigating the superiority of EPA-rich Omega-3 to placebo in the treatment of children and adolescents with pediatric major depressive disorder. The randomization included a minimization algorithm based on the following factors: site, age (8-12 vs. 13-18), gender (male vs. female), and hsCRP (<1 mg/l; 1-3 mg/l; >3mg/l). For sites offering both in- and out-patient care, in-/out-patient type was used as an additional minimization factor. The trial aimed to recruit children/teenagers between 8 and 18 years old with a primary diagnosis of major depressive disorder (DSM-IV, K-SADS-PL) and at least moderate depressive symptoms (CDRS-R ≥ 40).

In order to include a representative sample of moderately and severely ill children with major depressive disorders, the use of clinically required SSRIs is permitted. The anticipated proportion of patients receiving additional antidepressants at some point during follow-up is estimated to be around 30%. The use of additional antidepressants is expected to influence primary outcome measurements and be influenced by treatment group, with greater antidepressant use hypothesized in the control arm. Antidepressant use may therefore bias the estimation of the omega-3 treatment effect.

2 Scope of the statistical analysis plan

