where time t is considered a factor (while also investigating possibility of linearizing time effect) and randomized treatment group (intervention) and the interaction between randomized treatment group and time are included as fixed effects. The baseline values of the minimization factors age, gender, and hsCRP, as well as baseline antidepressant use and omega-3 index are included as covariates. The baseline outcome measure is modeled in the response, not as a covariate. The terms b_{i0} , b_{i1} , and b_{s0} represent participant-specific random intercepts and slopes and site-specific random intercepts. The random effects are assumed to be normally distributed and an unstructured covariance matrix will be assumed. The error term $\varepsilon_i(t)$ is assumed to be normally distributed with mean zero and variance σ^2 , independent of the random effects and is independent over time. An overall treatment effect for CDRS-R score at 36 weeks ($\beta_1 + \beta_{11}$) will be reported with a 95% confidence interval and corresponding p -value.

The competing survival models for time to event r (intervention dropout or study dropout) take the form:

$$\lambda_{ir}(t) = \lambda_{0r} \exp\{\gamma_1 \text{intervention} + \alpha_r m_i(t)\}$$

where the cause-specific Cox models include intervention as a time-independent effect and the estimated true trajectory of CDRS-R as a time-varying effect. The parameters α_r measure the strength of association between the longitudinal outcome and risk of the corresponding dropout event.

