7.1.2 Sensitivity analyses for the primary endpoint

1. **Typical ITT analysis:** In order to compare results with other trials, the linear mixed model part of the analysis model above will be applied to the full analysis set, with all participants analyzed as randomized. The data from intervention dropout participants will be used as observed, i.e, the outcomes observed while on non-randomized antidepressants will be used. The mixed model assumes that missing data is missing at random. This analysis is expected to be biased toward the placebo arm, as the number of participants requiring antidepressants is expected to be higher in the placebo arm and the additional antidepressant will improve outcomes.
2. **Modified ITT analysis:** The first sensitivity analysis will be repeated, but the data from intervention dropout participants will be considered missing in the mixed model upon non-randomized antidepressant initiation/dose increase. The responses of participants with missing data will be assumed similar to those with complete data and similar covariate characteristics. The bias resulting from imbalance in the use of non-randomized antidepressants across treatment groups is curtailed, but the amount of data available for analysis, and therefore power, is diminished.
3. **Typical PP analysis:** In order to address the efficacy estimand, the sensitivity analysis model above will be applied to all full analysis set data during which participants were 'on protocol'. This means the participants are adhering to the treatment they were randomized to and are not using additional antidepressants. Non-compliers and those taking non-randomized antidepressants are excluded completely (i.e., complete case analysis). This yields an estimate of efficacy that is unbiased under the MAR assumption. It assumes that participants with missing data (those with additional antidepressants and those not adhering to randomized treatment) would have had similar outcomes to participants completing the study in the same treatment arm and with similar baseline characteristics and score trajectories. However, the use of additional anti-depressants is not considered to be random across participants, but rather related to intermediate outcomes and possibly treatment assignment. Selection bias is then expected to affect this estimate. Additionally, the reduction in participants decreases the power to detect a treatment effect.

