7.2 Secondary endpoints

7.2.1 Confirmatory secondary endpoints

The binary confirmatory secondary outcomes include:

- **Remission**, defined as a CDRS-R total score < 28 at any time up until 36 weeks
- **Response**, defined as a 30% drop in CDRS-R total score at any time up until **12 weeks**
- **Intervention dropout**, defined as initiation of non-randomized antidepressant use while on trial for participants not on a non-randomized antidepressant at baseline or an increase in antidepressant dose while on trial for participants on a non-randomized antidepressant at baseline

Unadjusted proportions per treatment arm will be presented with 95% confidence intervals. To adjust for baseline antidepressant use, omega-3 index, and CDRS score, as well as the minimization factors age, gender, and hsCRP, these binary outcomes will each be assessed using log-binomial models with treatment arm as the effect of interest. Each model will be interpreted in terms of the adjusted risk ratio (RR) comparing the outcome probability in the omega-3 group to that in the placebo group ($RR_{\text{omega-3/placebo}}$). The null hypothesis that the risk ratio is equal to 1 (no difference in risk across treatment groups) will be rejected if the 95% confidence interval for the risk ratio does not include 1. If the 95% confidence interval for the risk ratio is above 1, omega-3 treatment will be considered superior.

These models will include data from all randomized participants and analyze the participant data according to the treatment arms participants were randomized to (as-randomized). Data after intervention dropout will be considered missing. Multiple imputation under MAR will be used to impute longitudinal CDRS-R scores for study and intervention dropouts before the binary outcomes are determined. MI will be performed separately within each treatment arm (White et al 2011) using imputation models containing the minimization factors, baseline antidepressant use and omega-3 index.

As for the primary outcome, a delta-based sensitivity analysis approach will be used to address MNAR. For analysis of intervention dropout, imputation is only needed for participants with study dropout before intervention dropout and no sensitivity analysis is planned.

The continuous confirmatory secondary outcomes include:

- self-reported **quality of life** measured by the KIDscreen-CAT-27 overall score at 36 weeks
- **Depression severity** measured by DIKJ at 36 weeks

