These continuous outcomes will each be assessed using ANCOVA linear regression models with the 36-week measurement as the outcome, treatment arm as the effect of interest, and the baseline measurement, antidepressant use, omega-3 index, CDRS-R score, and the minimization factors age, gender, and hsCRP as covariates.

The treatment coefficient denotes the mean difference in outcome score across the treatment groups. The null hypothesis that the mean scores are equal across treatment groups will be rejected

if the 95% confidence interval for the treatment group coefficient does not include 0. If the 95% confidence interval for the treatment group coefficient is above 0 for KIDscreen-CAT-27 (below 0 for DIKJ), omega-3 treatment will be considered superior with respect to its effect on quality of life (depressive symptoms).

These models will include data from all randomized participants and analyze the participant data according to the treatment arms participants were randomized to (as-randomized). Data after intervention dropout will be considered missing. Multiple imputation under MAR will be used to impute scores at 36 weeks for study and intervention dropouts. MI will be performed separately within each treatment arm (White et al 2011) using imputation models containing the minimization factors, baseline antidepressant use, omega-3 index, and baseline score. As for the primary outcome, a delta-based sensitivity analysis approach will be used to address MNAR.

Sub-domains will be described with tables or figures.

The final confirmatory secondary outcome is:

- the time on trial before initiation of new or increased antidepressant use (intervention dropout).

A Kaplan Meier approach will be used to estimate unadjusted median time to this event overall and per treatment arm. A log rank test will be used to compare time to intervention dropout across treatment arms.

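### Time to new or increased antidepressant use is the one confirmatory secondary endpoint tested without any baseline covariate; a pre-specified adjusted Cox model may add power and would supply an effect estimate

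*SAP*

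**What the plan says.** SAP 5.2.1 lists six confirmatory secondary endpoints. SAP 7.2.1 analyses three of them (remission, response, intervention dropout as yes/no) with log-binomial models: "To adjust for baseline antidepressant use, omega-3 index, and CDRS score, as well as the minimization factors age, gender, and hsCRP". It analyses KIDscreen-CAT-27 and DIKJ by ANCOVA, with "the baseline measurement, antidepressant use, omega-3 index, CDRS-R score, and the minimization factors age, gender, and hsCRP as covariates".

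For the sixth, time to intervention dropout, it says only this: "A Kaplan Meier approach will be used to estimate unadjusted median time to this event overall and per treatment arm", and then "A log rank test will be used to compare time to intervention dropout across treatment arms". It names no covariate, stratum or hazard ratio, and gives no reason for treating this endpoint differently.

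The longitudinal part of the primary model is adjusted too (SAP 7.1): "The baseline values of the minimization factors age, gender, and hsCRP, as well as baseline antidepressant use and omega-3 index are included as covariates". On allocation, SAP 1 states: "The randomization included a minimization algorithm based on the following factors: site, age (8-12 vs. 13-18), gender (male vs. female), and hsCRP". In-/outpatient type was a further factor at sites offering both kinds of care.

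**The concern.** Three features make an unadjusted test an odd choice here.

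- **Baseline severity is plausibly prognostic.** Protocol 3.1.2 says that antidepressants should, where possible, be kept for the more severe cases.
- **The event differs by baseline status.** For a patient not on an antidepressant at baseline it is a first prescription. For a patient already on one it is a dose increase. The two groups are pooled without stratification.
- **Age, gender and hsCRP were minimised on.** If factors balanced by design also predict the event, a test that ignores them tends to be conservative.

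The Cox part of the primary joint model does not fill the gap. Its log-hazard is γ₁·intervention + α·m(t), where m(t) is the current CDRS-R trajectory. So γ₁ is the treatment effect with current symptoms held fixed, not the total effect on antidepressant use. The SAP's general rule on adding imbalanced covariates applies to models, and a log-rank test has no place for them.

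At stake are some power on an endpoint with little to spare, and an interpretable effect size.

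**Working it through.** **1. Figures in the documents.** No power, event count or hazard ratio is stated for this endpoint. The nearest design figure, for response (SAP 6.2), reproduces: 60% v 40% at 80% power gives 97 per arm; 97/0.9 = 107.8, so 108 per arm and 216 in total.

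Inputs: two-sided alpha 5% (Protocol 11); 1:1 allocation (SAP 6); about 30% of patients with the event (SAP 1); target 220. Protocol 6.2 implies 225 + 20 = 245 randomised, and up to 245 + 20 = 265. Expected events are therefore 0.30 × 220 = 66, 0.30 × 245 ≈ 74 and 0.30 × 265 ≈ 80.

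**2. Power of the planned test.** Schoenfeld: power = Φ(½·√d·|ln HR| − 1.96). For d = 74 and HR 0.6: ½ × 8.602 × 0.511 − 1.96 = 0.24, which gives 59%. The hazard ratios are assumptions.

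| HR | 66 events | 74 events | 80 events |
|---|---|---|---|
| 0.5 | 80% | 85% | 87% |
| 0.6 | 55% | 59% | 63% |

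At HR 0.6, 80% power needs 4 × (1.96 + 0.842)² / (ln 0.6)² ≈ 121 events.

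**3. Effect of adjustment, by simulation.** The SD of the baseline covariates' joint log-hazard is not in the documents, so it is varied. SDs of 0.5, 0.8 and 1.0 mean hazard ratios of 1.65, 2.23 and 2.72 per SD of the risk score. Event times are exponential. Columns A and B fix week-36 risks at 22% v 38% (average 30%), with N = 220 and about 10% loss. A uses one known risk score (4,000 trials); B uses five estimated covariates (2,000 trials). Columns C to F fix the conditional hazard ratio, with N = 245, about 74 events, 15% study dropout and five estimated covariates (1,500 trials). In D and F the arms are pair-matched on the risk score, an idealised stand-in for minimisation. Entries are power in %, unadjusted → adjusted.

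| SD | A | B | C: HR 0.6, simple | D: HR 0.6, balanced | E: HR 0.5, simple | F: HR 0.5, balanced |
|---|---|---|---|---|---|---|
| 0 | – | 71→69 | 60→58 | 57→56 | 82→81 | 84→83 |
| 0.5 | 71→75 | 72→75 | 52→57 | 56→57 | 81→83 | 82→82 |
| 0.8 | 73→82 | 73→81 | 51→57 | 56→61 | 77→84 | 80→84 |
| 1.0 | 73→86 | 74→85 | 45→57 | 50→60 | 72→84 | 74→81 |

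Simulation error in C to F is about 1.0 to 1.3 points. The change across columns is about -2 to 0 points at SD 0, 0 to 5 at SD 0.5, 4 to 9 at SD 0.8 and 7 to 13 at SD 1.0.

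**4. Type I error (N = 245, error about 0.6 points).** With balanced arms, the log-rank rejected in 4.3%, 3.3% and 2.7% of null trials at SD 0.5, 0.8 and 1.0; the adjusted test rejected in 5.4% to 5.7%. With simple randomisation, the log-rank gave 4.7% to 5.7% and the adjusted test 4.9% to 6.3%. Conservatism therefore appears only when strong predictors are also well balanced. Pairing on the whole score exaggerates this, because baseline CDRS-R and antidepressant use were not minimisation factors.

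**5. Effect estimate.** A median requires the event-free curve to fall to 50%. At about 30% events overall it probably will not; even an assumed 38% risk in one arm leaves 62% event-free at week 36. SAP 7 says that results will generally be point estimates with 95% confidence intervals, but nothing else planned for this endpoint supplies one.

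**The case against.** The strongest reply is that the event already has an adjusted confirmatory test. WH 2a (Protocol 5.2) is about how many patients are put on antidepressants, and the log-binomial model for intervention dropout tests that with the full covariate set. A reader might infer that the log-rank is the trial's test of WH 2a. It is not; this endpoint adds timing. That stands, and it lowers the importance of the point.

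Second, a reader might infer that the log-rank is invalid or biased. It is neither, and it needs no covariate model. Marginal and covariate-conditional hazard ratios are different quantities, so a smaller marginal value is not an error.

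Third, a reader might infer that power is certainly being given away, or that the SAP itself says baseline severity drives antidepressant use. The SAP's sentence is "the use of additional anti-depressants is not considered to be random across participants, but rather related to intermediate outcomes and possibly treatment assignment", which concerns post-baseline outcomes. The support for baseline CDRS-R is the general statement in Protocol 3.1.2, and the entry criterion of CDRS-R at least 40 restricts the baseline range. Gains of 4 points or more throughout the table need an SD of about 0.8, which nothing in the documents establishes. What survives is plausibility, not a demonstrated loss.

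**Conclusion.** The inconsistency is a matter of text: five of the six confirmatory secondary endpoints are adjusted for baseline covariates, and this one is not, with no reason given. The planned test is valid. Adjustment would cost up to about 2 points of power if the covariates do not predict the event, and would gain up to about 13 if they predict it strongly. Both ends rest on the assumed hazard ratios, dropout and prognostic strengths above. If strongly prognostic factors are also well balanced, the unadjusted test is conservative, with type I error near 3%. The firmer gain is a hazard ratio with a confidence interval, where the current plan may report only a p-value. This is a worthwhile but minor improvement, and it does not threaten the trial's conclusions on antidepressant use.

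**What to change.** In SAP 7.2.1, before the analysts receive the randomisation code, make the confirmatory test for this endpoint the treatment term of a cause-specific Cox model. Stratify it by baseline antidepressant use, and adjust for baseline CDRS-R (continuous), age group, gender and hsCRP category. Report the hazard ratio with its 95% confidence interval, labelled as covariate-conditional. Keep the Kaplan-Meier curves and the unadjusted log-rank as supportive. If the code has already been released, Protocol 11.4.6 requires the adjusted model to be declared post hoc.

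State the choices on the remaining factors. In-/outpatient type can be considered as a further stratum. Site may be too thin: 66 to 80 events over seven recruiting centres is about 9 to 11 each. Omega-3 index should enter only if missing values are handled, because the blood sample it needs is optional (Protocol 9.2.2.4).

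The cost is one SAP sentence and one model. The minimisation factors are complete by design (SAP 7), and CDRS-R is scored at the baseline visit before randomisation (Protocol 9.3.2). Treatment, CDRS-R, age group, gender and two hsCRP terms make six parameters, or 66/6 = 11 events each. The price is reliance on a covariate model, a conditional rather than marginal hazard ratio, and the possible small loss of power noted above.

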7.2.2 Supportive secondary endpoints

Effect endpoints

- **Number of days in the hospital**
- **Outpatient service use**

These endpoints will be described using summary statistics across treatment arm.

Safety endpoints

- **Suicidal ideation** from baseline to week 36 will be modeled jointly by a linear mixed effects model for SIQ-Jr score over time combined with Cox regression for time to intervention and study dropout, analogously to the CDRS-R total score primary outcome model.
- **Serious adverse events** from baseline to week 36 will be tabulated per type and treatment arm using the safety analysis set. If appropriate, the difference in proportion (with 95% confidence interval) will be estimated.

8 Changes to the statistical analyses planned in the protocol

Version	Explanation
IICT submission	First version of study plan
Frontiers protocol	Study protocol after funding review and peer review, addition of concomitant treatment description, addition minimization factor for unit type (in-/outpatient), description of sensitivity analyses to account for antidepressant use
UZH protocol	Refinement of secondary (supportive/exploratory) outcomes and their analyses
Statistical analysis plan	Focusing the analysis plan on measures of efficacy and safety for reporting of primary trial results. Updating method for dealing with informative missingness.

9 References

N. M. Laird and J. H. Ware. Random-effects models for longitudinal data. *Biometrics* 1982; 38:963–74

R J A Little and L Yau. Intent-to-treat analysis for longitudinal studies with drop-outs. *Biometrics* 1999; 52:1324–33.

S Mazumdar and K S Liu and P R Houck and C F Reynolds. Intent-to-treat analysis for longitudinal clinical trials: coping with the challenge of missing values. *Journal of Psychiatric Research* 1999; 33:87–95

Michele L Shaffer and Vernon M Chinchilli. Including multiple imputation in a sensitivity analysis for clinical trials with treatment failures. *Contemporary Clinical Trials* 2007 28:130–137

Ian R. White and C Bamias and P Hardy and S. Pocock and J Warner. Randomized clinical trials with added rescue medication: some approaches to their analysis and interpretation. *Statistics in Medicine* 2001; 20:2995–3008.

R version and packages used to generate this report:

R version: R version 4.0.1 (2020-06-06)

Base packages: stats, graphics, grDevices, utils, datasets, methods, base

Other packages: pwr, readxl, reporttools, xtable, knitr

This document was generated on May 23, 2022 at 12:26.

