7.4 Criteria for Withdrawal/ Discontinuation of Participants

Clinicians/ treating doctors/ patients and their relatives can withdraw a patient at any time if they think it is in his best interest. To support clinicians in their decision making at what point a patients shall be withdrawn from the study for safety reasons, we defined following exit criteria.

Reasons to terminate a subject's participation:

- A subject withdraws her/his consent
- Non-compliance with medication (no intake of study medication for more than three out of seven days in two consecutive weeks)
- Daily omega-3 supplementation in addition to study medication (>600 mg combined EPA/DHA per day for more than one week)
- The clinician or investigator considers a subject's continued participation in the study to be unjustifiable on medical grounds (i.e. because of the emergence of another serious medical condition).
- The subject falls below a score of 40 on the Children's Depression Rating Scale at the end of the placebo lead-in phase.
- Acute Suicidality/ overt hostility: Clinicians and research assistants will monitor suicidality/hostility at each visit. If a clinician/ researcher considers the suicidal risk/ hostility as high requiring some sort of clinical action (e.g. a suicide watch plan as an outpatient, or restricted leave as an inpatient because of intense suicidal ideation/hostility), patients shall be withdrawn from the study if the clinician considers a potential connection with the study drug and a SUSAR shall be reported. The number and type of SUSARs will be compared between the treatment groups (active versus placebo).
- Intolerance to the study drug. Life-threatening side effect other than suicidality/ hostility (SUSAR): In case of an unexpected life-threatening side effect (e.g. a severe allergic reaction to one of the ingredients of the study medication), a patient must be withdrawn from the study.
- The development of a major axis one disorder listed under the exclusion criteria (e.g. a first psychotic or manic episode is considered as a serious adverse event).
- Unwanted but not life-threatening adverse events: If the side effect persists, the study medication shall be ceased and the patient discontinued due to lack of tolerability (an important further outcome criteria).

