8.7.2 Starting an antidepressant

Starting an antidepressant is not a withdrawal criterion, but will be considered as an outcome measure in data analysis (e.g. we assume that the omega-3 fatty acids group will need less antidepressants compared to the placebo group). In addition, we will run an analysis where we will multiply impute the data since starting antidepressants, with the aim to mimic observations one would have observed without taking antidepressants. We will consider the missingness generating mechanism to be “not at random” (MNAR). As the number of patients and the time on antidepressants is a secondary outcome criteria, this decision shall be made completely independent of the research team. In order to have sufficient power for this analysis, we will recruit up to 20 additional patients who do not start with antidepressant treatment in the first 6 weeks of the trial.

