9.2.4.3 Vital Signs

Vital signs will be assessed in the lead-in phase and again at the end of the study (week36) by the study nurse or investigator (e.g. heartbeat, blood pressure, body temperature, height and weight).

A drop-out visit shall be performed including documentation of reasons for drop out in case a patient drops out, or a parent / clinician / investigator withdraws a patient from the study. The drop-out visit will be performed at the earliest convenient time and will include an assessment of physical health and current medication use. Depressive symptoms will be assessed using the CDRS-R and the K-SADS-PL. In addition, psychosocial functioning will be assessed with a range of clinician rated scales (CGI-S/I, CGAS, HoNOSCA) and self-reported scales (DIKJ, BHS, BAI II, SIQ-Jr, PSS-10, Connor-Davidson Resilience Scale, SDQ, Insomnia Severity Index, IES-27-J). Patients will fill in the ASEC for assessing putative side effects. If the patient agrees, blood, urine, saliva and hair will be sampled, and in case no IQ test was done previously during the trial, a short IQ test will be performed.

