11.4.5 Safety Analysis

Safety and harms frequency data will be described based on actual treatment received using MedDRA (integrated in SecuTrial®) and the self-report side effect checklist (ASEC). The rate of harm- and suicide-related adverse events (e.g. SIQ-Jr) in each treatment group will be compared using χ^2 and Fisher exact tests, and ORs will be calculated to provide an indicator of relative risk of the active versus the placebo condition.

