5.2.2 Supportive secondary endpoints

Effect endpoints

- Number of days in hospital
- Lower outpatient service use

Safety endpoints

- Suicidal ideation (SIQ-Jr) from baseline to week 36 (measured at baseline, 6, 12, 24, and 36 weeks)
- Number of SUSARs from baseline to week 36

Statistical considerations

6 Sample size determination

The sample size calculations were performed for the primary outcome, as well as closely related secondary outcomes in order to ensure all questions of high interest are sufficiently powered. All calculations assume a parallel two-arm design with a 1:1 randomization ratio.

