7.1 Primary endpoint

- CDRS-R total score from baseline (post-placebo-lead-in) to week 36

The primary analysis consists of a joint model linking (1) a linear mixed effects model for CDRS-R total score over time with (2) a Cox proportional hazards model for the risk of the event new initiation of or increase in antidepressant use (intervention dropout) and (3) a Cox proportional hazards model for the risk of study dropout as a competing event. This assumes that whether a participant has missing data and at what time this occurs contains additional information that should be taken into account and corresponds to an MNAR missing data mechanism.

Participants are censored at whichever occurs first of: antidepressant initiation/increase, loss to follow up, consent withdrawal, and study exit due to non-adherence. Participants lost to follow up, withdrawing consent, and exiting the study (as per protocol) due to non-adherence are considered alike and these events considered one event type: study dropout.

The linear mixed effects model for the longitudinal CDRS-R total score outcome $Y_i(t)$ measured at time t for participant i takes the following form:

$$\begin{aligned}
 Y_i(t) &= m_i(t) + \varepsilon_i(t), \\
 m_i(t) &= \beta_0 + \beta_1 \text{intervention}_i + \beta_2 t_{base} + \beta_3 t_{6weeks} + \beta_4 t_{12weeks} + \beta_5 t_{24weeks} + \beta_6 t_{36weeks} \\
 &\quad + \beta_7 t_{base} * \text{intervention}_i + \beta_8 t_{6weeks} * \text{intervention}_i + \beta_9 t_{12weeks} * \text{intervention}_i \\
 &\quad + \beta_{10} t_{24weeks} * \text{intervention}_i + \beta_{11} t_{36weeks} * \text{intervention}_i \\
 &\quad + \beta_{12} \text{age}_i + \beta_{13} \text{gender}_i + \beta_{14} \text{hsCRP}_i \\
 &\quad + \beta_{15} \text{antidepressant} + \beta_{16} \text{omega-3 index} \\
 &\quad + b_{i0} + b_{i1}t + b_{s0},
 \end{aligned}$$

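### The SAP's only comparative SIQ-Jr analysis stops at antidepressant start or study dropout and, unlike the CDRS-R analysis, has no as-observed or delta analysis beside it

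*SAP*

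**What the plan says.** SAP 5.2.2 lists this safety endpoint as "Suicidal ideation (SIQ-Jr) from baseline to week 36 (measured at baseline, 6, 12, 24, and 36 weeks". SAP 7.2.2 analyses it with a "linear mixed effects model for SIQ-Jr score over time combined with Cox regression for time to intervention and study dropout", by analogy with the CDRS-R primary model. Section 7.2.2 gives no censoring rule of its own. The rule is in SAP 7.1: "Participants are censored at whichever occurs first of: antidepressant initiation/increase, loss to follow up, consent withdrawal, and study exit due to non-adherence".

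The protocol goes on collecting the score after these events:

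- Protocol 8.7.2: "Starting an antidepressant is not a withdrawal criterion, but will be considered as an outcome measure in data analysis". These participants therefore stay on the visit schedule in 9.1, which has SIQ-Jr at every study visit.
- Protocol 9.2.4.3 includes SIQ-Jr among the drop-out-visit instruments: "self-reported scales (DIKJ, BHS, BAI II, SIQ-Jr, PSS-10, Connor-Davidson Resilience Scale" and others. Sections 8.5 and 9.1 agree.

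The protocol also links worsening to both events. In 7.4, for acute suicidality or hostility that needs clinical action, "patients shall be withdrawn from the study if the clinician considers a potential connection with the study drug and a SUSAR shall be reported". In 8.7.1, lack of improvement or worsening leads the treating team to consider admission, an antidepressant, or both.

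The protocol has two SIQ-Jr comparisons of its own. Section 11.4.3 (WH5a) plans a t-test or Mann-Whitney test between arms. Section 11.4.5 plans chi-square and Fisher tests with odds ratios for harm- and suicide-related events, and names SIQ-Jr as an example. It opens with "Safety and harms frequency data will be described based on actual treatment received". Neither comparison states any censoring.

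**The concern.** Working hypothesis 5a (Protocol 5.4) is that omega-3 causes no drug-related SUSARs and, in particular, no rise in SIQ-Jr. Protocol 4.4 makes suicidal ideation a named safety concern because of what has been reported with SSRIs.

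For that question, the model stops using a participant's scores at events that worsening ideation can itself bring about. Suppose ideation rises between two visits and leads to an antidepressant or to withdrawal before the next one. The last score the model uses then predates the rise, although a later score may have been collected. A statement of no increase would rest on scores taken before anyone acted on a deterioration, and nothing in the SAP would test how far it depends on that.

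**Working it through.** The documents give no sample size, power or margin for SIQ-Jr, so there is no planned figure to reproduce. The check traces the text and then counts.

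**1. Does the censoring carry over?** Section 7.2.2 points to the primary model and names the same two dropout events. Section 7.1 censors at the first of them. Section 7.1.2 supports this reading: its analysis 1 is set apart by using scores after antidepressant start as observed. The censoring of SIQ-Jr is therefore an inference from two sections, but the natural one.

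**2. What does the joint model recover?** The hazard for event r is λ_ir(t) = λ_0r exp{γ_1·intervention + α_r·m_i(t)}, where m_i(t) is the modelled score trajectory. The event is allowed to depend on the trajectory, so this is more than plain truncation. But m_i(t) is estimated from scores before the event, and visits are 6 to 12 weeks apart (0, 6, 12, 24, 36). A rise after the last pre-event visit enters only by extrapolation.

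**3. Is the drop-out-visit score used?** The SAP does not say. The endpoint lists five nominal times and the fixed-effect time factor has five matching levels. The random slope uses t, however, and the SAP leaves open a linear time effect. Omission is the likely result but is not stated.

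**4. Is there another analysis?**

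| SAP analysis | CDRS-R | SIQ-Jr |
|---|---|---|
| Joint model, censored | yes (7.1) | yes (7.2.2) |
| As-observed mixed model | yes (7.1.2, no. 1) | no |
| Delta-based MNAR analysis | yes (7.1.2, no. 4) | no |
| Descriptive statistics by arm | yes (7) | yes (7); scores included not stated |

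Delta analyses also cover confirmatory secondary endpoints (7.2.1), but SIQ-Jr is supportive. The two protocol comparisons do not appear in the SAP, and the change lists in SAP 2 and 8 do not mention their removal.

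**5. How many contribute only a baseline score?** Inputs: 225 randomised and 21 dropouts before the first follow-up (Protocol 6.2); about 20 antidepressant starts before that visit (Protocol 6.3.2). The 20 are taken as belonging to the same 225.

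- Full overlap: 21/225 = 9.3%.
- No overlap: (21 + 20)/225 = 41/225 = 18.2%.

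**6. How many scheduled scores follow an antidepressant start?** This is an illustration under stated assumptions: 220 participants, four post-baseline visits each, the documents' 30% antidepressant use, and no study dropout.

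- Scheduled scores: 220 × 4 = 880.
- Starters: 0.30 × 220 = 66, of whom 20 start before week 6 and 46 later.
- Early starters lose 4 scores each: 20 × 4 = 80. Later starters lose 1 to 3 each: 46 to 138.
- Total: 126 to 218 of 880, or 14% to 25%. Study dropout among starters would lower this.

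**The case against.** The case for the plan has five parts.

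- **Serious events are counted elsewhere.** Withdrawal for suicidality under Protocol 7.4 requires a suspected drug link and triggers a SUSAR report. That section says SUSARs will be compared between arms. SUSARs are a listed safety endpoint (SAP 5.2.2). SAEs to week 36 are tabulated by arm in the safety set with no stated censoring (SAP 7.2.2). The data monitoring committee watches suicide attempts (Protocol 1.8). This stands. A reader might infer that suicidality as a whole escapes analysis; the documents do not support that.
- **The later scores may still be reported.** SAP 7 promises descriptive statistics by arm for all safety endpoints, and the SAP does not expressly delete the protocol's tests. So it goes too far to say that the scores are collected and never analysed. What stands is that the SAP specifies no comparative analysis that uses them.
- **Dropout is modelled as informative.** This stands, and the model is worth keeping. It narrows the gap to changes after the last pre-event visit.
- **The drop-out visit may not help.** Protocol 8.5 promises only an attempt, as soon as can be arranged, so some scores will be missing or late. That limits the gain but does not justify leaving the handling of obtained scores unstated.
- **As-observed scores can mislead.** The SAP expects more antidepressant use on placebo, and the protocol reports concern that SSRIs raise suicidal ideation. If both hold, later scores would raise the placebo mean and make omega-3 look safer. If antidepressants instead reduce ideation, the shift goes the other way. This stands, and it is why a reader should not infer that the as-observed analysis ought to replace the joint model. Nor does the phrase about actual treatment in Protocol 11.4.5 require that: it can simply mean an as-treated population.

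**Conclusion.** The concern holds in limited form. The only comparative SIQ-Jr analysis the SAP specifies ends at antidepressant start or increase, or at study dropout. Worsening can lead to either, and no sensitivity analysis tests the dependence on that choice. The protocol's two comparisons without stated censoring have dropped out of the SAP.

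On interim counts, 9% to 18% of 225 randomised participants would contribute only a baseline score. The range reflects unknown overlap and will move, because recruitment continued. The documents show the path from worsening to censoring but not how often it is taken, and the direction of any bias between arms cannot be determined.

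A reader might multiply the 30% antidepressant figure by the 10% loss figure to get a share of week-36 scores discarded. The documents do not support that. The two events are unlikely to be independent, and the 10% is a sample-size allowance for the responder comparison (SAP 6.2), not a forecast of dropout.

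**What to change.** In SAP 7.2.2:

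1. Keep the joint model, and state explicitly that SIQ-Jr is censored as in 7.1.
2. Add beside it an as-observed SIQ-Jr comparison by arm in the safety analysis set: the same mixed model without censoring, as in 7.1.2 analysis 1, on all SIQ-Jr values, including those after antidepressant start.
3. Enter the drop-out-visit score at its actual study day. The five-level time factor has no place for it, so state how time is coded. A continuous term, such as the log-days scale in Protocol 11.4.2, would serve.
4. Require both results to be reported before concluding that suicidal ideation did not increase.
5. Say whether the protocol's WH5a test and its 11.4.5 comparison are retained or replaced, and list this among the changes.

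The cost is SAP wording and one more model on data already scheduled for collection; trial conduct does not change. The downside is that scores after antidepressant start also reflect the antidepressant, and unequal use could move the comparison in either direction. Neither analysis should stand alone.
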